5.2 Inclusion Criteria

1. Adults (all genders) 21 to 75 years old.
2. Severe primary Alcohol Use Disorder (AUD) (≥ 6 DSM-5 AUD criteria) with or without other substance use disorders.
3. Participants are seeking treatment for their AUD (participants receiving medications or other therapy for AUD are eligible).
4. Participants have insight into their alcohol use disorder (score >26 on the recognition subscale of the Stages of Change Readiness and Treatment Eagerness Scale (SOCRATES V.8)).
5. Participant has advanced compensated alcohol-associated liver disease (ALD). Compensated is defined as asymptomatic per clinical evaluation (by hepatologist or internist). Advanced is defined as fibrosis stage ≥ 3 .
6. AUD is treatment refractory: unable to achieve sustained remission (>12 months) over the past 5 years, despite treatment attempts, with at least one treatment attempt involving completed residential or outpatient treatment program with pharmacotherapy, behavioral therapy, or both.
7. Stated willingness to comply with all study procedures and availability for the duration of the study.
8. Social support system and stable living arrangement to provide assurances that the subject will adhere to study requirements: family or friends who live with or near the subject, and can provide collateral information, monitor the subject's behavior, support, and encourage the subject to participate in follow-up visits and evaluations. This is evaluated by a neuropsychologist.
9. For females of reproductive potential: use of highly effective contraception for at least 4 weeks prior to DBS surgery and agreement to use such a method during study participation, and after study completion if they elect to keep the DBS system implanted and ON.

5.3 Exclusion Criteria

1. Pregnancy or lactation.
2. Non-English speaking.
3. AUD treatment with another investigational drug or other intervention within 3 months.
4. History of primary psychosis or Bipolar I disorder per the psychiatric evaluation or SCID-5 measure.
5. History of severe personality disorder that could interfere with study participation (e.g., antisocial personality disorder) per the psychiatric evaluation, neuropsychological evaluation, or SCID-5 measure.
6. IQ <75 as measured by WASI (Wechsler Abbreviated Scale of Intelligence) (evaluated by a neuropsychologist).
7. History of suicidal attempts in the past 5 years or current suicidal thoughts per psychiatric evaluation and Columbia-Suicide Severity Rating Scale (C-SSRS).
8. Decompensated ALD: clinically obvious ascites, hepatic encephalopathy, jaundice episodes, large esophageal varices with or without variceal bleeding, hepatorenal syndrome, per the clinical evaluation (by hepatologist or internist).
9. Coagulopathy: INR > 1.4 , aPTT > 40 s, platelets $< 100,000$, abnormal platelet or fibrinogen function tests.

10. Current clinically significant medical or neurologic disease that affects brain function (e.g., recent stroke, myocardial infarction, seizures not due to alcohol withdrawal).
11. Clinically significant abnormality on structural brain MRI scan.
12. Life expectancy less than 18 months per the clinical judgement during medical evaluation (e.g., no terminal cancers).
13. Any labeled DBS contraindication or inability to have brain MRI: certain pacemakers, metal in body, inability to undergo awake operation, significant cardiac or other medical risk factors for surgery, infection, and coagulopathy.
14. History of liver transplant.

5.4 Recruitment Methods

We will recruit patients who have severe primary AUD and advanced compensated (asymptomatic) alcohol-associated liver disease (ALD). Severe AUD is defined as meeting 6 or more of the DSM-5 criteria [141]. Advanced ALD refers to fibrosis stage 3 or 4 diagnosed by liver US or liver fibrosis blood test. .

Recruitment will mainly be from inpatient services, outpatient clinics, Electronic Health Record (EHR), and research registries throughout the UPMC network. We will also use IRB-approved flyers for recruitment. Recruitment will be limited to facilities within 1-hour driving distance from UPMC Presbyterian Hospital, where all study evaluations and interventions will be performed, in order to limit the travel burden on participants for frequent assessment visits that are required for study enrollment. In order to alleviate financial burden, participants will be compensated for travel, parking, and food.

Inpatient recruitment will be led by [name] (Psychiatry Consult Liaison, Department of Psychiatry) and [name] (Addiction Medicine Consult Service, Department of Medicine), who are primarily in charge of evaluating and treating all SUD patients, including AUD, throughout the UPMC system. The psychiatry Consult Liaison service sees around 1100 admitted patients per year, ~20% of whom are primary AUD patients (~220 AUD patients per year). The Addiction Medicine Consult Service sees about 1200 admitted patients per year, a third of whom are primary AUD patients (~400 AUD patients per year). They, or their team members, as well as the study coordinator will identify and prescreen potential participants from the above inpatient services and clinics listed below. If potential participants are identified, the study coordinator will reach out to the treating physician who is asked to discuss the study with the potential subject and to request the subject's permission to be contacted by the study team. Outpatient recruitment will include subjects from multiple clinics within the UPMC network, including the UPMC Alcohol-Related Liver Disease Clinic (Department of Medicine), Center for Psychiatric and Chemical Dependency Program Services (Department of Psychiatry) where [name] and her team members see patients, Ambulatory Detoxification Clinics, and other clinics involved with AUD patients like the Alcohol Highway Safety Program (Department of Psychiatry). Identified patients will be provided the contact information for the study or will be approached by the study coordinator or a study investigator. Recruitment from the EHR will be enacted via Research Recruitment Alerts (RRAs) within the EpicCare interface. These alerts are triggered during clinical encounters in which the patient meets certain inclusion criteria for the study. Physicians may then assess the patient's interest in study participation and respond in the EHR accordingly. Study coordinators will be automatically notified of potential interested participants and may reach out by phone or email. The study team may prescreen the EMR prior to calling potential interested participants. The study will also leverage the Pitt+Me Research Participant Registry at UPitt to recruit participants to the study. Pitt+Me Registry is a recruitment tool run by the Clinical and Translational Science Institute (CTSI) at UPitt (see CTSI letter of support), which currently enrolls subjects who self-

report an interest in participating in research studies at UPitt and agree to be contacted regarding studies for which they could be eligible. Pitt+Me uses a proprietary algorithm that generates study matches based on self-reported interests and ICD-19/10 diagnoses from the UPMC electronic medical records (>6 million patients). Pitt+Me also uses social media to further engage the community. Currently, Pitt+Me enrolls more than 260,000 self-identified potential research participants. Of these, more than 164,000 are within the study's age range (21 - 75 years), 1,832 of whom have an alcohol-related disorder diagnosis in their electronic medical records, and 224 of whom also have alcohol-induced liver, pancreatic, or gastric disease (42 of these participants are Black). We will post our study descriptions and contact info to the Pitt+Me website. Interested subjects can pre-screen and potentially eligible participants will be referred to our study through the Pitt+Me Study Portal Dashboard.

If recruitment numbers are lacking with the above strategies, we will rely on CTSI recruitment facilitators who can help identify recruitment tools and resources in the local community, and assist with using social media to promote our research study. We will also rely on flier advertisements (e.g., on buses, AA meeting sites, hospitals lobbies), and digital advertisements using social media (e.g., Twitter, Facebook, podcasts).

Participants will be compensated for each visit; parking and food expenses during each visit will be covered, and they will additionally receive compensation for time spent on study activities. They will receive \$200 for every full day evaluation visit (e.g., screening visit, baseline, 6-, and 12-month assessments), \$100 for every follow up visit, and \$200/day for every admission day to the hospital (during implantation or explantation surgery). They will also receive up to \$70 for cognitive tasks (CGT and BART), \$20/day for parking and \$30/day for food. Participants will also receive a sum of \$750 bonus upon completion of the study.

5.5 Screen Failures

Patients who have signed consent, but do not meet participation criteria will not be allowed to continue in the study; signed consents will be stored under double lock. During the in-person screening visit, patients' mental status will be evaluated by a psychiatrist, and then patients will undergo detailed neuropsychological evaluation to determine their competency and whether their informed consent is valid. If they are determined to not be competent, then their signed consent will be considered voided, and they will likewise not be allowed to continue in the study. If a patient later has indications that they now meet inclusion criteria (e.g., if platelets were 90,000 due to acute alcohol effects and then increased to 110,000), then they may be considered for re-screening and re-consent, before progressing to study participation.

6 Study Device

6.1 Device Selection

The hardware for DBS therapy will include the Percept PC Neurostimulator and the SenSight DBS Directional Leads, both from Medtronic (device brochures are provided in Appendix B). The SenSight electrodes will be surgically implanted bilaterally in the limbic pallidum in the brain, and the Percept stimulator will be implanted into the chest wall. The Percept stimulator will deliver electrical stimulation into the limbic pallidum via the SenSight electrodes. Both devices are FDA approved for Parkinson's disease, essential tremor, and epilepsy. They are also approved via Humanitarian Device Exemption in refractory obsessive compulsive disorder, dystonia.

Percept neurostimulator is the only stimulator that allows recording local field potentials from the area of stimulation. SenSight directional leads were specifically chosen because they allow directional stimulation, minimizing off-target stimulation and associated side-effects.

We have obtained a Right of Reference letter from Medtronic and we will obtain an Investigational Device Exemption from the FDA for the present study.

The intervention will last the entirety of the study, from the time of implantation and throughout the follow-up evaluations. Patients will be evaluated at the end of the study to determine whether intervention will continue after the study. Intervention may be cut short in cases of premature explantation (e.g., adverse events or elective study withdrawal – discussed below).

Implantation will be performed in two stages. First, the DBS directional leads will be neurosurgically implanted that is the same as standard of care DBS implantations for Parkinson's disease (except that the target here is the LP), with an inpatient stay of two to three days. To best guide the electrode placement to our area of interest, we will use each patient's structural MRI and white matter tractography in conjunction with volumetric computed tomography (CT) scan. Second, the neurostimulator will be implanted in an outpatient surgical procedure, 7-10 days after lead implantation; patients will be discharged the same day.

DBS optimization: Three weeks after the neurostimulator is implanted, we will optimize the DBS settings. DBS titration will be based on stimulation parameters used in previous OCD and SUD studies [101, 144-146]. We will start by screening each contact for clinical effect guided by craving scores and side effects such as photopsia (optic tract), tetanic contraction (posterior limb of internal capsule), or behavioral change (anterior limb of internal capsule). While it is unclear if LP DBS results in acute effects on alcohol craving, we will attempt to optimize DBS settings while measuring craving using the ACQ-SF-R questionnaire and Cue Reactivity task (we will monitor for acute changes in craving scores on the ACQ-SF-R and CR scales with the different DBS settings). If no clear clinical effect is observed, we will identify the optimal electrode contact and stimulation parameters using Lead-DBS software [147, 148]: we will 1) reconstruct and localize the electrodes and 2) simulate the VTiA at different contacts as described in our previous study [69]. DBS will be turned ON in a standard monopolar mode at 135 Hz at the primary and other DBS contacts while monitoring for side effects. We will use pulse width 90-150 μ s and intensity 2-6 V, which proved to be the most effective in OCD and SUD DBS studies [101, 144, 145]. We will use symmetric biphasic pulses, shown to be more efficacious in ameliorating PD and tremor symptoms than other configurations [37, 149-151]. Stimulation intensity will be increased in small increments until we observe side effects or a voltage limit of 10V, whichever is lower, which will be considered the ceiling of stimulation. We will then reduce stimulation intensity to 70% of ceiling voltage.

DBS titration will occur over the course of 2 days. After optimization, DBS will be turned ON continuously at the optimized settings. We will continue to titrate the DBS settings during follow-up visits if participants experience delayed AE or continue to crave and relapse.

At the end of the study, if a participant experienced a significant clinical benefit (improvement of their AUD defined as significant reduction in alcohol use), and since it is not clear whether turning the DBS system OFF (or explanting it) will result in relapse, the participant will have the option to 1) keep the DBS system implanted and ON, 2) keep the DBS system implanted but OFF, or 3) have the DBS electrodes and neurostimulator explanted. All patients will have 3 follow-up visits (monthly) after the study completion. For options 1 and 2, we will continue to follow up the participants yearly (or more frequently if needed) for 5 years, and possibly for a longer duration. These follow-ups will involve standard of care clinical evaluations in the Neurology and Psychiatry clinics of the study investigators ([name] for Neurology and [name] for psychiatry). During these visits, we will continue to screen for potential adverse effects, conduct neurological and psychiatric evaluations, including assessing their alcohol use. If the DBS did not improve a participant's AUD, we would explant the DBS electrodes and neurostimulator. For explantation, participants will be admitted to the hospital and the DBS system will be explanted. Participants will be monitored overnight in the hospital, and will receive a post-operative CT scan to ensure there are no complications from the surgery. These participants will be referred to the outpatient psychiatry clinic for standard of care follow ups.

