4) Repeatable Battery for the Assessment of Neuropsychological Status (RBANS) which includes list learning, story learning, copying a complex figure, line orientation task, picture naming task, coding task, digit span forward task, delayed recall of the learned list, delayed recall of the learned story, and delayed recall of the copied figure (~30 min): this assessment provides a measure of language and visuospatial functions.

5) Controlled Oral Word Association Test (~5 min): this provides a measure of verbal fluency. The timed task requires the participant to name as many words as possible that begin with a specified letter.

6) Digit Span from the Wechsler Adult Intelligence Scale- 4th Ed (backward and sequencing) (~5 min): this test provides a measure of working memory.

7) Vocabulary, Similarities, and Matrix Reasoning of the Wechsler Abbreviated Scale of Intelligence (~20-40 min): this provides a measure of language and executive functions.

- **Cognitive and behavioral tasks:** these tasks are used to measure cognitive and behavioral processes strongly associated with vulnerability to relapse to alcohol like cue reactivity, reward processing, and various aspects of impulsivity. These tasks are administered via a computer screen and the participants are required to press a button or keyboard stroke, or fill a paper questionnaire after presentation of cues on the screen. These tasks are described in detail in the Research Strategy Section and include:
 - 1) Alcohol Cue Reactivity task (CR).** This task measures reactivity and craving in response to alcohol cues. Participants will be seated in front of a computer screen and will complete a 12-trial computer-automated CR procedure. Each trial consists of a relaxation prompt, a picture cue presentation (alcohol vs. neutral; the alcohol cues are informed by subjects' drinking preferences collected during the psychiatric evaluation), and a final prompt to fill out post-trial self-report ratings of craving, mood, and arousal based on how he/she felt while focusing on that picture. The CR task lasts approximately 15 minutes.
As exposure to alcohol cues could cause craving, anxiety, and discomfort. Experienced Psychiatry Department study staff will be present at all times during cue exposure and will provide support and conduct relaxation techniques until craving returns to pre-exposure levels.

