12.6 Exploratory Analysis

Cognitive and behavioral tasks

The outcomes of the cognitive and behavioral tasks (Cue Reactivity (CR), Card Guessing Task (CGT), Delay Discounting task (DD), Balloon Analog Risk Task (BART), and Stop Signal Reaction Time task (SSRT)) are collected at baseline and at the 6-, and 12-month time points. These outcome measures include:

- craving, positive affect, negative affect, calm, and excitement scores for CR
- β - and γ -spectral power for CGT
- discounting rate (k) for DD
- adjusted pumps for BART
- SSRT

H5: LP DBS will normalize reward processing (reduce baseline and increase event-related spectral power in the β - and γ -range) and reduce alcohol CR, temporal discounting, risk taking, and motor impulsivity post-DBS compared to baseline.

Analysis of H5: The outcome measures will be analyzed like the PET measure of target engagement measures, using one-way RM ANOVA between baseline values, DBS-ON at 6 months, and DBS-ON at 12 months, with post-hoc comparisons to the baseline.

Intra-operative neurophysiology

H6. Different neuronal populations in the LP encode rewarding vs. aversive stimuli and these neurons respond differently for alcohol vs. neutral cues.

H6.1: a population of LP neurons will show significant increase in neuronal firing during reward expectation.

H6.2: a different population of LP neurons will show significant increase in responding during loss expectation.

Analysis of H6.1 and H6.2: A 2-way repeated-measure ANOVA will be used to compare the firing frequency of the different epochs (first epoch represents baseline firing) in different trial types (win vs. neutral vs. loss) (dependent variable = firing rate, factor 1 = epoch, factor 2 = trial type), with post-hoc comparisons. In task responsive neurons, we expect to see significant epoch X trial type interaction, as well as significant effect of epochs and trial types.

13 Data and Safety Monitoring

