12.6 Exploratory Analysis

Cognitive and behavioral tasks

The outcomes of the cognitive and behavioral tasks (Cue Reactivity (CR), Card Guessing Task (CGT), Delay Discounting task (DD), Balloon Analog Risk Task (BART), and Stop Signal Reaction Time task (SSRT)) are collected at baseline and at the 6-, and 12-month time points. These outcome measures include:

- craving, positive affect, negative affect, calm, and excitement scores for CR
- β - and γ -spectral power for CGT
- discounting rate (k) for DD
- adjusted pumps for BART
- SSRT

H5: LP DBS will normalize reward processing (reduce baseline and increase event-related spectral power in the β - and γ -range) and reduce alcohol CR, temporal discounting, risk taking, and motor impulsivity post-DBS compared to baseline.

Analysis of H5: The outcome measures will be analyzed like the PET measure of target engagement measures, using one-way RM ANOVA between baseline values, DBS-ON at 6 months, and DBS-ON at 12 months, with post-hoc comparisons to the baseline.

Intra-operative neurophysiology

H6. Different neuronal populations in the LP encode rewarding vs. aversive stimuli and these neurons respond differently for alcohol vs. neutral cues.

H6.1: a population of LP neurons will show significant increase in neuronal firing during reward expectation.

H6.2: a different population of LP neurons will show significant increase in responding during loss expectation.

Analysis of H6.1 and H6.2: A 2-way repeated-measure ANOVA will be used to compare the firing frequency of the different epochs (first epoch represents baseline firing) in different trial types (win vs. neutral vs. loss) (dependent variable = firing rate, factor 1 = epoch, factor 2 = trial type), with post-hoc comparisons. In task responsive neurons, we expect to see significant epoch X trial type interaction, as well as significant effect of epochs and trial types.

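### The Cue Reactivity task is both an exploratory H5 outcome and a tool for comparing DBS settings, so any fall in ratings from repetition could not be told apart from a DBS effect

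*Protocol*

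**What the plan says.** The CR task has two uses in the plan.

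- **As an outcome.** Protocol section 12.6 lists "craving, positive affect, negative affect, calm, and excitement scores for CR" among the task measures, which "are collected at baseline and at the 6-, and 12-month time points". H5 predicts that DBS will "reduce alcohol CR, temporal discounting, risk taking, and motor impulsivity post-DBS compared to baseline". The analysis in both the protocol and the SAP is "using one-way RM ANOVA between baseline values, DBS-ON at 6 months, and DBS-ON at 12 months", with post-hoc comparisons to baseline.
- **As a titration instrument.** Protocol section 6.1 (DBS optimization) states that "we will attempt to optimize DBS settings while measuring craving using the ACQ-SF-R questionnaire and Cue Reactivity task" and adds that "we will monitor for acute changes in craving scores on the ACQ-SF-R and CR scales with the different DBS settings". Titration takes two days and may be resumed at follow-up visits, among other reasons when a participant still craves and relapses.

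Section 7.4 describes the task: participants "complete a 12-trial computer-automated CR procedure" of about 15 minutes, with alcohol and neutral pictures, the alcohol ones informed by the person's own drinking preferences.

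In Appendix A the CR row carries five marks, one of them footnoted, where BART, Delay Discounting and SSRT carry three each. One footnote to the table allows for use as needed with side effects or intense cravings. The columns are broken in the text available, so which visits the extra marks belong to cannot be confirmed.

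Neither document mentions separate pictures for titration and outcome sessions, a record of how many CR runs each person has had, or a term for prior exposure in the model. Section 12.6 does not say whether the CR score is an alcohol-minus-neutral difference.

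**The concern.** The baseline CR score follows no scheduled run of the task. The month-6 score follows the baseline run and whatever runs were used to compare settings. Ratings may fall because the person has seen the pictures and filled in the scales before. Such a fall would lie between baseline and month 6, in the direction that H5 predicts for craving. There is one arm and there are three participants, so nothing in the design or the model separates repetition from stimulation.

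Exposure may also be unequal. Someone who keeps craving may be titrated again and, if the Appendix A footnote applies to the CR row, see the task more often. Exposure would then be tied to clinical response, and three participants cannot support an adjustment for it.

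At stake is whether a CR signal can be interpreted when later efficacy studies, the protocol's stated ultimate goal, are planned.

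**Working it through.** The documents give no power, error or exposure figure for H5, so there is nothing to reproduce. Three checks follow.

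**1. CR runs before each outcome session.** Let k be the number of titration runs before month 6. The value is not stated. Comparing scores between settings needs k of at least 2.

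- Baseline: 0 earlier runs.
- Month 6: 1 + k, so at least 3. Without CR in titration it would be 1.
- Month 12: 2 + k plus any later re-titration runs, so at least 4. Without CR in titration it would be 2.

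Some repetition is unavoidable. The avoidable part is k, and it falls almost wholly on one side of the baseline comparison. Each run adds 12 trials, neutral pictures included: 12 × 2 = 24 at the minimum; if k were 4, 8 or 16 (assumed), 48, 96 or 192.

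**2. Other cue exposure.** Section 7.4 also sets the Card Guessing Task (up to 240 trials), BART (up to 350) and Delay Discounting (two runs of up to 150) among alcohol and neutral cues. Section 12.6 places all three at the same assessments:

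240 + 350 + 2 × 150 = up to 890 trials, or 890 + 12 = 902 with CR.

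If each trial shows a cue and the maximum is run, the extra CR trials are 24/902 = 2.7%, 48/902 = 5.3%, 96/902 = 10.6% or 192/902 = 21.3% of one assessment's cue trials. The documents do not say whether pictures are shared between tasks. A count of CR trials alone therefore does not measure cue exposure. What titration specifically adds is repetition of the CR pictures and of the CR rating procedure.

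**3. What a shift would do to the test.** Assume no DBS effect, a pure habituation shift, and two-sided 0.05 (the plan states no level for H5).

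- *Post-hoc comparison with baseline*, taken as a paired t-test with n = 3 and df = 2. The noncentrality is d × √3, where d is the shift in SDs of the paired difference. The chance of a significant fall is 2.5% at d = 0, 7.9% at 0.5, 17.9% at 1, 47.1% at 2 and 74.5% at 3.
- *RM ANOVA*, 3 participants × 3 times, F on 2 and 4 df, 200,000 simulations, with the shift present at months 6 and 12 and measured in residual SDs. Rejection is 5.0% at 0, 6.9% at 0.5, 13.3% at 1, 39.2% at 2 and 71.0% at 3.

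The size of d is not in the documents, so these are ranges and not estimates. Section 12.1 also mentions exact methods for small samples. An exact signed-rank test on three pairs has a smallest two-sided p of 2/2³ = 0.25. Under that choice the bias would show in the estimated change and not in a p-value.

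**The case against.** The strongest reply is that the size, and even the direction, of habituation is undocumented. Section 7.4 says that cue exposure could cause craving and says nothing about its waning. Contact screening is guided by craving scores and side effects, and the ACQ-SF-R, about five minutes long, could supply those scores without a full CR run at each setting. Titration falls at about days 50-51 and the 6-month assessment at about days 230-233, so any effect must last roughly 180 days. Four of the five CR scores are not craving.

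All of that stands as a limit on size. It does not remove the dual use, which section 6.1 states. A fall is at least plausible: each trial begins with a relaxation prompt, and staff use relaxation techniques after cue exposure until craving settles.

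A second reply is that the remedy is partial. A separate titration set does not prevent habituation to alcohol images in general, to the rating procedure or through the other cue tasks, and the reserved set is itself repeated at months 6 and 12. This is right, which is why the fix also asks for a log and a stated limitation. Nor would an alcohol-minus-neutral score solve it, because habituation specific to the alcohol pictures would remain.

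A third reply is that an exploratory, open-label result in three people, all referred for standard AUD treatment (section 5.1), cannot be attributed to DBS anyway. That limits the importance of the point. It is not a reason to leave in a bias that is easily reduced.

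**Conclusion.** The point holds in a limited form. The plan uses one task both to compare settings and to test H5, and a decline from repetition could not be distinguished from a DBS effect. This rests on the text of sections 6.1 and 12.6 and on the absence of any separation of stimuli or record of runs. The minimum of two titration runs is inferred from scores being compared across settings. Re-use at follow-up is likely from Appendix A but not confirmed.

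A reader might infer more, and the documents do not support it:

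- That participants see the cues many times more often than at baseline. No run count is given, and the 12 CR trials are not a participant's whole baseline cue exposure, given up to 890 further cue-linked trials per assessment.
- That craving would fall by some calculable percentage without DBS. Any such figure multiplies three unknowns: runs, fall per run and share persisting to month 6.
- That the same or a narrow set of pictures is reused. Neither re-use nor pool size is stated.

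The size is therefore unknown. Only an exploratory outcome is affected. The primary safety, tolerability and feasibility endpoints do not use it. It is a cheap improvement to make, not a flaw in the trial's main purpose.

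**What to change.** - Reserve a fixed, beverage-matched picture set for the baseline, 6-month and 12-month CR sessions, and use a separate beverage-matched set for titration and re-titration.
- State in section 12.6 of the protocol and SAP that the H5 CR analysis uses only the reserved set.
- Log and report each participant's number of CR runs before each outcome session.
- Interpret the CR result descriptively, with residual habituation (to alcohol images in general, the rating procedure and the other cue tasks) named as a limitation.

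The cost is selecting a second picture set, one sentence in 12.6 and a per-participant count. It adds no visits or staff and changes no stimulation setting or clinical rule. The small downside is that titration scores would not be directly comparable with outcome scores. It has to be in place before the first baseline session, because a picture already used in titration cannot be reserved afterwards.

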6.3 Intervention Delays and Modifications

If a participant experiences adverse effects related to stimulation, we will modify the stimulation parameters until the adverse effects have resolved.

If the adverse effects are refractory to DBS optimization, this will call for early explantation of the DBS system. There will not be modifications to the study device itself (both electrodes and stimulator are implanted).

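### Protocol section 6.1 sets stimulation intensity at 2-6 V, but its own titration rule gives up to 7 V, and the text does not say which governs

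*Protocol*

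**What the plan says.** All the relevant text on voltage is in the protocol, section 6.1, under DBS optimization. In the order in which it appears:

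- The paragraph opens by naming its source: "DBS titration will be based on stimulation parameters used in previous OCD and SUD studies".
- It then fixes two parameters in one sentence, as what the study will use: a pulse width of 90-150 μs and "intensity 2-6 V, which proved to be the most effective in OCD and SUD DBS studies".
- It describes a step-up search in each participant: "until we observe side effects or a voltage limit of 10V, whichever is lower, which will be considered the ceiling of stimulation".
- It derives a level from that search: "We will then reduce stimulation intensity to 70% of ceiling voltage".
- The paragraph that follows carries the result forward: "After optimization, DBS will be turned ON continuously at the optimized settings".
- Later changes are allowed, with no voltage range given: "We will continue to titrate the DBS settings during follow-up visits if participants experience delayed AE or continue to crave and relapse".

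Section 6.3 adds that, for stimulation-related adverse effects, "we will modify the stimulation parameters until the adverse effects have resolved". Section 9.1 likewise allows reprogramming or switching off when side effects occur. Neither section states a voltage. The SAP covers only the statistical sections and says nothing on device settings.

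**The concern.** The first voltage statement gives a range for the study. The later steps define the setting as a percentage of a ceiling that may reach 10 V. Nothing links the two, and for the highest permitted ceilings the percentage rule produces a setting outside the range.

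Stimulation intensity is the exposure in this trial. Safety and tolerability are primary outcomes (section 12.3), and the study-level stopping criteria turn on events related to limbic pallidum stimulation (sections 11.1 and 11.3). Section 14.3 rules out protocol deviations and has their occurrence monitored. If a participant is programmed above 6 V under the 70% rule, one sentence of section 6.1 makes that setting compliant and another makes it a deviation. With three participants, one such case would be a third of the cohort.

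**Working it through.** The protocol states no resulting voltage, so there is no figure of its own to reproduce. The check is whether the titration rule stays inside the stated range.

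**Inputs, all from section 6.1**

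- Stated range: 2 to 6 V.
- Ceiling *C*: the voltage at which side effects appear, or 10 V, whichever is lower.
- Fraction of the ceiling retained: 0.70.

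**Formula**

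Setting = 0.70 × *C*, with *C* ≤ 10 V.

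**Where the rule leaves the range**

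- Top: 0.70 × *C* = 6 gives *C* = 6 / 0.70 = 8.57 V.
- Bottom: 0.70 × *C* = 2 gives *C* = 2 / 0.70 = 2.86 V.

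**Settings at selected ceilings**

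| Ceiling (V) | 0.70 × ceiling (V) | Within 2-6 V? |
|---|---|---|
| 2.5 | 1.75 | No |
| 3 | 2.10 | Yes |
| 5 | 3.50 | Yes |
| 8 | 5.60 | Yes |
| 8.5 | 5.95 | Yes |
| 9 | 6.30 | No |
| 9.5 | 6.65 | No |
| 10 | 7.00 | No |

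**Size of the mismatch at the top**

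- Span of ceilings affected: 10 − 8.57 = 1.43 V.
- Largest excess: 7.0 − 6.0 = 1.0 V, or 7.0 / 6.0 − 1 = 16.7%.

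**Low end.** A ceiling below 2.86 V gives a setting below 2 V. This is the weaker half of the point. Such a low ceiling can arise only from side effects, and the provisions for side effects in sections 6.1, 6.3 and 9.1 allow parameter changes without stating a voltage floor, so they partly cover it.

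**Does any other text settle the top end?** The follow-up titration sentence in section 6.1 gives no range or cap. Sections 6.3 and 9.1 respond to side effects, whereas the conflict concerns a participant who shows none up to a high voltage. Titration for continued craving or relapse is not driven by side effects and has no stated bound, so the same gap carries into follow-up. No other section gives a voltage range or an order of precedence. The device manuals in Appendix B are listed by title only and could not be checked; the protocol does not point to them as settling this.

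**The case against.** The best case for the present text is that it can be read in sequence. The paragraph says that titration draws on earlier studies, and the 2-6 V clause carries its own justification from those studies. The steps for the individual participant come afterwards. On that reading 2-6 V is background or a starting range, and the later rule sets the level. The protocol never calls 6 V a limit or maximum; it uses such words only for side effects and 10 V. It can also be said that continuous stimulation is at the optimized settings, and that optimization draws on contact screening, craving scores and, where no clear effect is seen, electrode simulation, so equating it with the 70% result is an inference.

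The consequence is also bounded. A setting above 6 V arises only after the participant has passed 8.57 V without observed side effects, and it is then 30% below the level reached. Phone checks, reprogramming and a patient off-switch follow.

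Part of this stands. The sequential reading is plausible, the excess is small and conditional, and no figure in the protocol is miscalculated: this is a point of internal consistency. But the reading is not compelled. The sentence is written as what the study will use, and the same verb governs pulse width, for which the protocol gives no other rule; treating the voltage as merely indicative would make the pulse width indicative too. The 70% step is the only rule in the text that yields a voltage for continued use. A participant without side effects up to 10 V is a planned branch of the procedure, and following the rule there takes the setting outside the stated range. The safeguards limit harm but do not say which sentence applies.

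**Conclusion.** The concern holds. For ceilings above 8.57 V and up to the permitted 10 V, the 70% rule and the stated 2-6 V range cannot both be followed; the rule exceeds the range by at most 1.0 V (17%). Between 2.86 V and 8.57 V there is no conflict. Below 2.86 V there is a lesser mismatch, partly covered by the side-effect provisions.

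This rests on two readings: that 2-6 V is a study setting, as its wording indicates, and that the 70% result is the level carried into continuous stimulation. If the sponsor meant the range only as a starting point, the conflict disappears, but the protocol has to say so. The frequency cannot be estimated from the documents. Sample size, endpoint definitions and planned analyses are untouched. It should be fixed because it concerns the only study intervention in a trial with safety as a primary outcome.

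**What to change.** Reconcile the sentences in section 6.1 so that one rule governs programmed intensity. The revised text should state:

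1. whether 2-6 V is a starting range, a working range, or a bound on the 70%-of-ceiling result;
2. which statement takes precedence when the two differ, at either end of the range;
3. whether the same rule applies to titration at follow-up visits, including titration for continued craving or relapse.

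The choice is clinical and belongs to the sponsor; no setting or rule is proposed here. The cost is one or two sentences in section 6.1, with no change to design, sample size or analysis.
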